10.2.2. Analysis of Efficacy for key secondary Endpoint

• Analysis per patient (based on 4-8 lipomas/nodules per patient)

The two-sample T-test or Non-parametric Wilcoxon-Mann-Whitney Rank sum test for independent samples (as is appropriate) will be applied for testing the statistical significance of the difference between study groups in percent reduction of lipoma/nodule pain at day 84 after injection vs. baseline.

Analysis of covariance (ANCOVA) model will be applied in order to identify covariate parameters suspected as related to reduction in lipoma/nodule pain and in order to test the differences in percent reduction of lipoma/nodules pain between the treatment groups adjusted to the above covariates.

• Analysis per lipoma/nodule (based on 4-8 lipomas/nodules per patient)

The MMRM model (Mixed-effect model for repeated measures) will be applied for analyzing the difference between the groups in percent reduction in local pain score at day 84 vs. baseline between the study groups adjusted for the above covariates as appropriate.

10.2.3. Analysis of other Secondary Endpoints

Analysis of Safety

Safety data from the study will be summarized descriptively by treatment. The incidence of intolerable side effects will be presented by treatment.

Descriptive statistics will be calculated for quantitative data and frequency counts and percentages will be provided for categorical data. The nature, frequency, seriousness, severity and relation to study drug of AEs will be tabulated for all subjects combined and by treatment. Change-from-baseline values for vital signs, clinical laboratory and ECG will be summarized. Draize scores will be presented in tabular format by visit and treatment. Serious adverse events (SAEs) will be described in narratives as part of the study report.

Analysis of Efficacy

Clearance of nodules: (Analysis per Lipoma based on 4-8 lipomas per patient):

95% Confidence Interval (CI) will be calculated for the proportion of responding nodules (response will be defined as achieving a reduction in lipoma height of at least 75% vs. baseline) by study groups.

GEE (Generalized Estimating Equations) model will be applied for testing the statistical significance of the difference in percent of responding nodules (nodules with at least 75% clearance at day 84 vs. baseline) between the study groups, with adjustment to suspected confounders.

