	GEE (Generalized_Estimating Equations) model will be applied for testing the statistical significance of the difference in percent of responding nodules (nodules with at least 75% clearance at day 84 vs. baseline) between the study groups, with adjustment to suspected confounders.
Study Duration	Study duration for each patient will be 3.5 months, including enrollment, treatment and follow-up period.
	Each subject will participate in the study for up to 98 days as part of this protocol.
	Placebo subjects who continue to the open label extension part may participate for an additional 84 days.
Study Sites	4

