5.2.2. Study Randomization

Subjects will be randomized to each study group, i.e., investigational therapy or control, according to a predefined randomization scheme in a ratio of 1:1 (active:placebo) among the 4 clinical sites. The investigational therapy group will be treated with RZL-012 and the control group will be treated with the same formulation (vehicle) as with RZL-012, absent active medication.

Assignment to study group will be disclosed only after subject eligibility is confirmed and immediately before treatment initiation. The investigator and the clinical staff will be masked to the treatment. The subjects will also be blinded and will not know whether he or she is injected with active or placebo treatment.

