10.3. SAMPLE SIZE JUSTIFICATION

Based on primary endpoint:

The rationale for sample size calculation was based on interim data from Raziel's open label phase 2a study (Study #RZL-012-FD-P2aUS-001) in which reduction in lipoma/nodule height of about 55% was demonstrated in the treatment group. Raziel's phase 2a study did not include a placebo group but studies reported by other groups (15,16) show an average reduction from baseline in lipoma/nodule height of about 7% in the placebo group. Taking these numbers into consideration Raziel expect an effect size of 0.96 (effect size = expected effect size in treated (0.55) – expected effects size in placebo group (0.07)/expected standard deviation (0.5)).

Sample size justification:

A sample size of 19 in each group (total sample size of 38) will have 80% power to detect a difference in means of 48 (the difference between a Group 1 mean, μ 1, of 55 and a Group 2 mean, μ 2, of 7) assuming that the common standard deviation is 50 using a two-group t-test with a 0.05 two-sided significance level.

Based on key secondary endpoint:

The rationale for sample size calculation was based on data from our open label phase 2a study (Study #RZL-012-FD-P2aUS-001) in which reduction in lipoma/nodule pain score of about 76% was demonstrated in the treatment group. Our phase 2a study did not include a placebo group but pain studies reported by other groups (17) show a range of reduction in pain score from +10% - 60% in the placebo group. Based on Geography, study size and length we selected an expected reduction from baseline of 25% in lipoma pain in our placebo group. Taking these numbers into consideration we expect an effect size of 1.02 (effect size = expected effect size in treated (0.76) – expected effects size in placebo group (0.25)/expected standard deviation (0.5)).

Sample size justification:

A sample size of about 19 in each group (total sample size of 38) will have 80% power to detect a difference in means of 51 (the difference between a Group 1 mean, μ 1, of 76 and a Group 2 mean, μ 2, of 25) assuming that the common standard deviation is 50 using a two-group t-test with a 0.05 two-sided significance level.

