10.4. STATISTICAL ANALYSIS

10.4.1. General

All measured variables and derived parameters will be listed individually and, if appropriate, tabulated by descriptive statistics.

For categorical variables summary tables will be provided giving sample size, absolute and relative frequency and 95% CI (Confidence Interval) for proportions by study group.

For continuous variables summary tables will be provided giving sample size, arithmetic mean, standard deviation, coefficient of variation (CV%), median, minimum and maximum and 95% CI (Confidence Interval) for means of variables by study group.

All tests will be two-tailed, and a p value of 5% or less will be considered statistically significant.

Subject Disposition

A detailed description of subject accountability including count of subjects included, exposed, completed (i.e., subjects who complete the study treatment) and discontinued along with the main reason for discontinuation will be generated for each treatment group and for all subjects. All withdrawals from the study, taking place on or after study drug injection, will be fully documented in the body of the Clinical Study Report.

Note that the actual study duration is for a period of maximum 3.5 months, with efficacy analyses being conducted at Day 28, 56, and 84 visits.

At the end of the period, when the follow up of subjects will be completed, randomization codes will be opened.

Placebo subjects who would like to be treated with RZL-012 at the end of the study will be injected (within a period of 30 days from codes opening) and will be followed up for efficacy for additional 84 days. The efficacy information that will be collected for the open label extension study will not be included in the randomized double blinded study report but will be used for internal information.

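### The nodule-level responder GEE has only 38 patients as clusters and no stated small-sample method: its error rate can exceed 5% with ordinary robust Wald tests, and a logit fit has no finite treatment estimate if no placebo nodule responds

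*Combined protocol and SAP*

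**What the plan says.** For the endpoint on nodules losing at least three quarters of their height by Day 84, Section 10.2.3 plans a confidence interval per arm and one hypothesis test: "GEE (Generalized Estimating Equations) model will be applied for testing the statistical significance" of the difference between arms, "with adjustment to suspected confounders". The synopsis says the same: a GEE "model will be applied for testing the statistical significance of the difference in percent of responding nodules". Response is set as follows: "response will be defined as achieving a reduction in lipoma height of at least 75% vs. baseline".

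Section 10.4.1 fixes the threshold: "All tests will be two-tailed, and a p value of 5% or less will be considered statistically significant". Section 10.3 gives the size of the trial: "A sample size of 19 in each group (total sample size of 38) will have 80% power". Section 2.3 allows 4 to 8 injected nodules per subject, preferably 6. Section 10.5 rules out imputation, so the number of patients analysed can only fall.

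The plan does not state the link, working correlation, type of standard error, small-sample correction, reference distribution, Wald or score test, covariates, or what to do if an arm has no responders. It gives no assumed responder rates. The primary and key secondary endpoints have a per-patient test (Sections 10.2.1 and 10.2.2). This endpoint does not.

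**The concern.** The robust (sandwich) variance of a GEE is justified for many clusters. With few clusters it is biased downward, and each added patient-level covariate makes this worse. The clusters here are patients, so the effective number is 38 however many nodules are measured. A nominal 5% Wald test may then reject too often under no effect.

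The second issue is a zero cell. If no placebo nodule reaches the threshold, a logit model has no finite treatment coefficient. Software may still print one, with a tiny p-value. That could happen when the drug works and placebo does nothing. A responder claim could therefore rest on an inflated test or on a meaningless fit, and choosing a remedy after unblinding would be data-driven.

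**Working it through.** **1. The plan's own figure.** Difference 48, SD 50, so the effect size is 48/50 = 0.96. A two-sided 5% t-test with 80% power needs 18.05 per arm, rounded up to 19. Power at 19 is 82.1%. The stated 19 per group reproduces.

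**2. Responder rates implied by those inputs.** Section 10.3 says other groups' studies "show an average reduction from baseline in lipoma/nodule height of about 7% in the placebo group", and assumes an active mean of 55 and a common SD of 50. Treating a nodule's percent reduction as normal:
- placebo: P(Z ≥ (75 − 7)/50) = P(Z ≥ 1.36) = 8.7%
- active: P(Z ≥ (75 − 55)/50) = P(Z ≥ 0.40) = 34.5%
- placebo with the phase 2a per-lipoma SD of 44.1 (Section 1.2.2): 6.2%
- placebo with an assumed SD of 30: 1.2%; with 25: 0.3%

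**3. Error rate under no treatment effect.** The simulation used 38 patients, 4-8 nodules each (mostly 6), beta-binomial responses and a logit GEE with exchangeable working correlation. Within-patient correlations of 0.1, 0.3 and 0.5 and covariate counts of 0, 2 and 4 are assumptions. There were 4,000 runs per setting, and 15,000 in some. Monte Carlo error is about 0.2-0.5 points.

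Ordinary robust Wald z test, range over the correlations, among fits that converge:
- no covariates: 5.4-5.6% at a responder rate of 34.5%, 6.0-6.7% at 20%, 6.1-8.2% at 8.7%, 4.8-6.0% at 5%, 0.6-2.1% at 2%
- two covariates: 6.3-8.6% at rates of 8.7% and above, 5.8-7.5% at 5%, 3.0-4.3% at 2%
- four covariates: 7.3-10.7% at all rates; at 2%, counting non-estimable runs as non-rejections, 3.0-4.9%

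Alternatives at rate 8.7% and correlation 0.3:

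| Test | No covariates | 2 | 4 |
|---|---|---|---|
| Ordinary robust Wald z | 7.3% | 8.6% | 9.6-10.7% |
| Kauermann-Carroll, t reference | 5.6% | 5.7% | 5.3-5.4% |
| Mancl-DeRouen, t reference | 5.0% | 3.9% | 2.4-2.7% |
| Robust score | 4.4% | 5.1% | 5.9-6.1% |

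Elsewhere the score test reached 6.8% with four covariates and fell below 5% at low rates.

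**4. Probability of no placebo responder.** Take 19 patients with 6 nodules each, rate p and correlation ρ. Put a = p(1 − ρ)/ρ and b = (1 − p)(1 − ρ)/ρ. The probability is [∏ (b + k)/(a + b + k), k = 0 to 5]^19. For ρ from 0.1 to 0.5:
- p = 8.7%: 0.03-1.6%
- p = 5%: 1-9%
- p = 2%: 16-39%
- p = 1%: 40-63%

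Worked case, p = 2% and ρ = 0.3: a = 0.0467, b = 2.2867, and the result is 0.276.

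**5. What the failure looks like.** In one simulated data set with 34 of 115 active nodules responding and no placebo responders, standard software returned a placebo log-odds of −26.6 with a standard error of 0.000002. The treatment coefficient was 25.7, with a printed p of 0. These values are meaningless. The robust score statistic on the same data was finite (chi-square 12.4).

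**6. The patient-level test.** A Wilcoxon test on each patient's proportion of responding nodules rejected 4.3-5.2% under no effect at rates of 5-34.5%, and 1.1-3.3% at 2%. Power at 34.5% versus 8.7% was 79-97% over the correlations. At 34.5% versus 2% it was at least 99%, and the test rejected in every replicate with no placebo responder.

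**The case against.** The strongest reply is that the plan commits to neither ordinary Wald tests nor a logit link. A robust score test fits its wording equally well, is near nominal in most settings and stays finite with no placebo responders. This stands: a reader might infer that the planned test does exceed 5%, but the documents support only that it can, because they leave the choice open.

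A reader might also infer from the 7% placebo mean that a placebo arm without responders is likely. The same section assumes an SD of 50, and the two together imply 8.7% responders and less than a 2% chance of none. The larger probabilities need true rates of 1-2%, which no section gives. The reply has a limit. The SD of 50 is a common value for both arms, no placebo SD is reported, and mean 7 with SD 50 would put P(Z ≥ 93/50) = 3.1% of placebo nodules beyond 100% reduction, which is impossible. The 8.7% may therefore be too high.

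The two problems also mostly arise at different responder rates. Inflation appears mainly at 8.7% and above, and zero cells mainly near 1-2%, where the Wald test with no or two covariates is conservative. They should not be read as joint features of one test. Because the true rate is unknown, each still needs an answer in advance.

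**Conclusion.** The point holds in limited form. With ordinary robust Wald tests, the responder GEE would run at about 5.5-8% unadjusted and 6-11% with two to four covariates, at responder rates of 8.7% or more. The plan calls for adjustment, so the adjusted range is the more relevant one. At a rate near 2% without covariates there is no inflation. A logit fit has no finite treatment estimate if no placebo nodule responds: below 2% probability on the plan's own mean and SD, 16-39% at an assumed 2% rate.

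The within-patient correlations, the covariate counts and the normal model for nodule reductions are assumptions, because the documents give none of them. Severity is low. This is a non-key secondary endpoint, and the primary and key secondary endpoints already have patient-level tests.

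**What to change.** In Section 10.2.3 and the synopsis, before unblinding:

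- Make the formal test a Wilcoxon or permutation test on each patient's proportion of nodules with at least 75% reduction, in line with the per-patient tests of the primary and key secondary endpoints.
- Keep the GEE as supportive. State the link and working correlation, and use Kauermann-Carroll standard errors with a t reference and a small covariate set named in advance. Mancl-DeRouen errors are not an equal substitute here, since they become conservative under adjustment. Kauermann-Carroll does not cure a zero cell, so say that no odds ratio will be reported if an arm has no responders.
- Alternatively, keep the GEE as the formal test and specify a robust score test, again with few named covariates.
- Use one responder threshold throughout: Sections 3.3 and 10.1 require more than 75%, Section 10.2.3 at least 75%.

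The cost is SAP wording, with no change to data collection or sample size. The downside of the patient-level test is that patients with 4 and with 8 nodules count equally, which may lose a little efficiency.

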10.3. SAMPLE SIZE JUSTIFICATION

Based on primary endpoint:

The rationale for sample size calculation was based on interim data from Raziel's open label phase 2a study (Study #RZL-012-FD-P2aUS-001) in which reduction in lipoma/nodule height of about 55% was demonstrated in the treatment group. Raziel's phase 2a study did not include a placebo group but studies reported by other groups (15,16) show an average reduction from baseline in lipoma/nodule height of about 7% in the placebo group. Taking these numbers into consideration Raziel expect an effect size of 0.96 (effect size = expected effect size in treated (0.55) – expected effects size in placebo group (0.07)/expected standard deviation (0.5)).

Sample size justification:

A sample size of 19 in each group (total sample size of 38) will have 80% power to detect a difference in means of 48 (the difference between a Group 1 mean, μ 1, of 55 and a Group 2 mean, μ 2, of 7) assuming that the common standard deviation is 50 using a two-group t-test with a 0.05 two-sided significance level.

Based on key secondary endpoint:

The rationale for sample size calculation was based on data from our open label phase 2a study (Study #RZL-012-FD-P2aUS-001) in which reduction in lipoma/nodule pain score of about 76% was demonstrated in the treatment group. Our phase 2a study did not include a placebo group but pain studies reported by other groups (17) show a range of reduction in pain score from +10% - 60% in the placebo group. Based on Geography, study size and length we selected an expected reduction from baseline of 25% in lipoma pain in our placebo group. Taking these numbers into consideration we expect an effect size of 1.02 (effect size = expected effect size in treated (0.76) – expected effects size in placebo group (0.25)/expected standard deviation (0.5)).

Sample size justification:

A sample size of about 19 in each group (total sample size of 38) will have 80% power to detect a difference in means of 51 (the difference between a Group 1 mean, μ 1, of 76 and a Group 2 mean, μ 2, of 25) assuming that the common standard deviation is 50 using a two-group t-test with a 0.05 two-sided significance level.

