placebo group. Based on Geography, study size and length we selected an expected reduction from baseline of 25% in lipoma pain in our placebo group. Taking these numbers into consideration we expect an effect size of 1.02 (effect size = expected effect size in treated (0.76) – expected effects size in placebo group (0.25)/expected standard deviation (0.5)). Sample size justification: A sample size of about 19 in each group (total sample size of 38) will have 80% power to detect a difference in means of 51 (the difference between a Group 1 mean, μ_1 , of 76 and a Group 2 mean, μ_2 , of 25) assuming that the common standard deviation is 50 using a two-group t-test with a 0.05 wo-sided significance level.
difference in means of 51 (the difference between a Group 1 mean, μ_1 , of 76 and a Group 2 mean, μ_2 , of 25) assuming that the common standard deviation is 50 using a two-group t-test with a 0.05
Descriptive Statistics:
All measured variables and derived parameters will be listed individually and, if appropriate, abulated by descriptive statistics.
For categorical variables summary tables will be provided giving sample size, absolute and relative frequency and 95% CI (Confidence Interval) for proportions by study group.
For continuous variables summary tables will be provided giving sample size, arithmetic mean, standard deviation, coefficient of variation (CV%), median, minimum and maximum and 95% CI (Confidence Interval) for means of variables by study group.
All tests will be two-tailed, and a p value of 5% or less will be considered statistically significant.
The data will be analyzed using the SAS ® version 9.4 (SAS Institute, Cary North Carolina).
Analysis of Efficacy for Primary Endpoint
• Analysis per patient (based on 4-8 lipomas/nodules per patient)
The two-sample T-test or Non-parametric Wilcoxon-Mann-Whitney Rank sum test for independent samples (as is appropriate) will be applied for testing the statistical significance of the difference between study groups in percent reduction of lipoma/nodule height at day 84 after injection vs. baseline.
Analysis of covariance (ANCOVA) model will be applied in order to identify covariate parameters suspected as related to reduction in lipoma/nodule height and in order to test the differences in percent reduction of lipoma/nodules height between the treatment groups adjusted to the above covariates.
• Analysis per lipoma/nodule (based on 4-8 lipomas/nodules per patient)

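### Key secondary power is stated as 80%, but the plan's own inputs give 86.4% with 19 per arm

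*Combined protocol and SAP*

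**What the plan says.** Section 10.3 (Sample size justification) and the Sample Size part of the synopsis each give two parallel justifications, one per endpoint.

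- **Key secondary (pain).** The treated mean comes from the open-label phase 2a study, where a "reduction in lipoma/nodule pain score of about 76% was demonstrated in the treatment group". The placebo mean is a chosen "expected reduction from baseline of 25% in lipoma pain in our placebo group". From these the plan says "we expect an effect size of 1.02". It concludes that "about 19 in each group (total sample size of 38) will have 80% power to detect a difference in means of 51", "assuming that the common standard deviation is 50 using a two-group t-test with a 0.05 two-sided significance level". The synopsis makes the same claim: "will have 80% power to detect a difference in means of 51".
- **Primary (height).** With 19 per group and the same SD, test and alpha, the plan "will have 80% power to detect a difference in means of 48" (55 against 7, effect size 0.96).

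Section 10.4.1 confirms two-tailed testing at 5%. The documents state no alpha split and no dropout allowance, and the synopsis counts 38 evaluable subjects in a 1:1 ratio.

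**The concern.** The two power statements differ only in the difference to be detected, 48 against 51. With N, SD, test and alpha fixed, power rises strictly with that difference, so the two figures cannot both equal 80%. This can be seen without any calculation.

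Pain is the key secondary endpoint and has its own sample size justification, which should be reproducible from its own inputs. As it stands, a reader cannot tell whether the power is wrong or whether one of the printed inputs is not the one used. The question is a real one here, because the placebo response was selected by the sponsor from a wide published range. A reader who trusts the 80% would also take the risk of missing the assumed pain effect to be 20%.

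**Working it through.** **Inputs (Section 10.3; same values in the synopsis).** Treated mean 76, placebo mean 25, difference 76 − 25 = 51, common SD 50, 19 per arm, two-group t-test, two-sided alpha 0.05.

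**Effect size.** (76 − 25)/50 = 1.02, which matches the plan.

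**Formula.** Exact power of the two-sample t-test with n per arm:

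- degrees of freedom = 2n − 2
- noncentrality = (difference/SD) × √(n/2)
- power = P(|T| > critical t), where T is noncentral t

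**Key secondary, n = 19.** Degrees of freedom = 36. Noncentrality = 1.02 × √9.5 = 3.144. Critical t = 2.028. Power = **86.4%**, type II error 13.6%. The normal approximation gives 88.2%, further from 80%.

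**Primary, n = 19, for comparison.** Effect size (55 − 7)/50 = 0.96. Noncentrality = 0.96 × √9.5 = 2.959. Power = **82.1%**.

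**Is 80% a target reached by the smallest N?**

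| n per arm | Primary (difference 48) | Key secondary (difference 51) |
|---|---|---|
| 16 | 74.8% | 79.7% |
| 17 | 77.5% | 82.2% |
| 18 | 79.9% | 84.4% |
| 19 | 82.1% | 86.4% |

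For the primary endpoint, yes: 19 is the first n to pass 80%. For the key secondary, no: 17 per arm (34 in total) is enough.

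**What would make 80% true at 19 per arm?** The effect size would have to be 0.934, a difference of 46.7 at SD 50. Changing one input at a time:

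- SD: 51/0.934 = 54.6 instead of 50
- placebo reduction: 76 − 46.7 = 29.3% instead of 25%
- treated reduction: 25 + 46.7 = 71.7% instead of 76%

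**Unstated variants that come near 80%.** Two-sided alpha 0.025 gives 78.6%. About 15% dropout gives 80.1%. A Wilcoxon test at its worst-case relative efficiency of 0.864 gives 80.8%. The sample size text mentions none of these; it names the t-test at 0.05.

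**The case against.** The strongest reply is that 80% is a target and both sentences are true as lower bounds, since 19 per arm gives 82.1% and 86.4%. The printed 80% is not the exact power for the primary endpoint either. The pain sentence also says about 19, where the primary sentence says 19, and never claims to be the minimum. This softens the point but does not remove it. The text does not say at least 80%, it fixes the total at 38, and even 18 per arm gives 84.4%.

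A second reply is that nothing follows for the trial: the error is conservative, and N, test and alpha are unaffected. That is correct and limits the weight of the point.

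A third is that the plan never says which endpoint sets N. True, but it follows from the stated inputs: the primary needs 19 per arm and pain needs 17.

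A fourth is that 86% is itself a best case. Section 10.2.2 allows a Wilcoxon test instead of the t-test, Section 4.4 does not replace subjects who withdraw after injection, and Section 10.5 plans no imputation. This part stands: a corrected figure should carry its conditions.

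**Conclusion.** The stated power is wrong as written. On the plan's own inputs it is 86.4%, so the printed figure is 6.4 percentage points too low, in both Section 10.3 and the synopsis. The result assumes 19 evaluable subjects per arm, SD 50, a true difference of 51, and the t-test at two-sided 0.05. It takes those inputs as given and does not judge whether they are realistic.

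The adequacy of 38 subjects is not in question. That the 80% was carried over from the primary endpoint is a plausible explanation, but the documents do not show it. The correction is worth making because the figure is checkable, is wrong in two places and costs almost nothing to put right.

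**What to change.** Keep 38 subjects. Replace the key secondary power sentence in Section 10.3 and its copy in the synopsis with wording such as:

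> The 19 evaluable subjects per group required for the primary endpoint give about 86% power for a between-group difference of 51 points in mean percent pain reduction (76 versus 25), with a common SD of 50 and a two-sample t-test at the two-sided 5% level.

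If 80% came from other inputs, such as a dropout allowance, a different alpha or a larger SD, state those inputs in both places instead.

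The cost is one sentence, changed twice. There are no extra patients and no change to N, the test or alpha.
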